## **OL Zavegepant Treatment Compliance**

OL zavegepant treatment compliance categories are defined as follows for relevant protocol deviations (see Sections 6.2.4.1 and 9.1):

- OL zavegepant capsule count compliance < 80% from OL zavegepant start to later of last scheduled OLE Phase visit or OL zavegepant end. Capsule count compliance is derived as 100 × actual cumulative OL zavegepant capsule count/required cumulative OL zavegepant capsule count, where
  - Actual cumulative OL zavegepant capsule count is derived by summing the {number of days × number of capsules taken per day} across records with complete study medication start date and valid OL wallet ID.
  - Required cumulative OL zavegepant capsule count is derived as {OL maxdate OL zavegepant start date + 1} where
    - OL maxdate is defined as the latest of the (1) scheduled Weeks 14, 16, 20, 24, 28, 32, 36, 40, 44, 48, 52, 56, 60, and 64/EOT visit dates, and (2) OL zavegepant end date. Scheduled visits are identified from visit labels from the Visit Date CRF, and therefore exclude those containing "unscheduled" in the visit label.
    - The required number of capsules per day is based on the DB treatment group; see "DB Treatment Compliance".
- > 1 OL zavegepant capsule taken on any 1 day. This is determined from either of the following:
  - Records with complete study medication start date, valid OL wallet ID, and number of capsules taken per day > required number of capsules per day.
  - Overlapping records with valid OL wallet ID (see Section 9.4).
- OL zavegepant start date before DB study drug end date. Defined as OL zavegepant study drug start date ≤ DB study drug end date.
- OL zavegepant taken but DB study drug never taken. Defined as nonmissing OL zavegepant start date and missing DB study drug start date.

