#### 6.2.4 Protocol Deviations

#### 6.2.4.1 Relevant Protocol Deviations

The frequency table of relevant protocol deviations are provided as the number and percentage of subjects in deviation categories by as-randomized treatment group, zavegepant pooled, placebo pooled, and overall for the full analysis set. Results are shown by deviation type (eligibility, subject management), category, and subcategory in the order specified in Section 9.1. Results for all relevant protocol deviation categories and subcategories are displayed, even those with 0 counts, unless specified otherwise.

A by-subject listing of relevant protocol deviations is provided for the full analysis set. This includes deviation type, category, and subcategory, which are additional sorting variables.

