## **DB Study Drug Exposure**

The table of DB study drug exposure is provided descriptively by treatment group, zavegepant pooled, and placebo pooled for the DBT safety analysis set, and summarizes the following parameters descriptively as continuous or categorical variables:

- Time on DB study drug (weeks), derived as (DB study drug end date DB study drug start date + 1)/7
- Time on DB study drug (weeks) categories:  $< 2, \ge 2$  to  $< 4, \ge 4$  to  $< 6, \ge 6$  to  $< 8, \ge 8$  to  $< 10, \ge 10$  to  $< 12, \ge 12$
- Cumulative DB study drug exposure (mg), derived by summing {number of days × number of capsules taken per day × dose} across records with complete study medication start date and valid DB wallet ID
  - Number of days for a record is derived as imputed study medication end date study medication start date + 1.
  - The dose is 25 mg if the kit type identifier is DB zavegepant 100 or 200 mg; otherwise, the dose is 0.
- Average DB study drug exposure (mg per day), derived as cumulative DB study drug exposure/time on DB study drug (days)
- Total DB study drug exposure (capsules) summed across all subjects, derived by summing cumulative DB study drug exposure across all subjects
- Total DB study drug exposure (patient-years), derived by summing (DB study drug end date
   DB study drug start date + 1)/365.25 across all subjects.

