## 6.2.6.2 Measurements of Treatment Compliance

## **DB** Treatment Compliance

DB treatment compliance categories are defined as follows for relevant protocol deviations (see Sections 6.2.4.1 and 9.1):

- DB study drug taken but not randomized
- DB capsule count compliance < 80% from DB study drug start to later of last scheduled DBT Phase visit or DB study drug end/OL zavegepant start. Capsule count compliance is derived as 100 × actual cumulative DB capsule count/required cumulative DB capsule count, where
  - Actual cumulative DB capsule count is derived by summing the {number of days × number of capsules taken per day} across records with complete study medication start date and valid DB wallet ID.
    - Number of days for a record is derived as imputed study medication end date study medication start date + 1.
  - Required DB cumulative capsule count is derived as {DB maxdate DB study drug start date + 1} × {required number of capsules per day}, where
    - DB maxdate is defined as the latest of the (1) scheduled Week 2, 4, 8, and 12/EOT visit dates, and (2) DB study drug end date. Scheduled visits are identified from visit labels from the Visit Date CRF, and therefore exclude those containing "unscheduled" in the visit label.
    - If DB maxdate  $\geq$  OL zavegepant start date, then DB maxdate is set to OL zavegepant start date -1 day.
    - The required number of capsules per day is 4 for subjects in the zavegepant 100 mg or matching placebo group, and 8 for subjects in the zavegepant 200 mg or matching placebo group.
- More than the required number of DB capsules per day taken on any 1 day. This is determined from either of the following:
  - Records with complete study medication start date, valid DB wallet ID, and number of capsules taken per day > required number of capsules per day.
  - Overlapping records with valid DB wallet ID (see Section 9.4).
- Incorrect DB study drug taken
  - All the time. Defined as as-treated treatment group not equal to as-randomized treatment group, i.e., either of the following:
    - Subjects randomized to zavegepant who took  $(1) \ge 1$  capsule from a DB placebo wallet, and (2) no capsules from a DB zavegepant wallet
    - Subjects randomized to placebo who took  $(1) \ge 1$  capsule from a DB zavegepant wallet, and (2) no capsules from a DB placebo wallet.

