## **8 CONTENTS OF REPORTS**

All TLFs described in this SAP are produced for the LSLV final CSR (see Section 1.2).

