  - OL zavegepant capsule count compliance < 80% from OL zavegepant start to later of last scheduled OLE Phase visit or OL zavegepant end
  - o More than the required number of OL zavegepant capsules taken on any 1 day
  - o OL zavegepant start before DB study drug end
  - OL zavegepant taken but DB study drug never taken
- eDiary usage compliance < 80% from DB study drug start to later of last scheduled DBT Phase visit or DB study drug end/OL zavegepant start (see Section 6.2.6.2)
- Prohibited non-study medications, defined as any of the following subcategories:
  - Atypical antipsychotics, divalproex, valproic acid, or valproate taken on or after informed consent #
  - o Butterbur root or extract taken up to 14 days before randomization or afterward
  - Calcitonin gene-related peptide (CGRP) antagonist biologic or small molecule taken on or after informed consent #
  - o Ergotamine taken on or after informed consent
  - Lamotrigine taken on or after informed consent
  - o Narcotic (barbiturate or opioid) taken up to 2 days before randomization or afterward #

For the subcategories marked with "#", preferred names are displayed alphabetically as additional subcategories. Medications taken up to X days before a reference date or afterward are defined as those with imputed medication start date or imputed end date  $\geq$  reference date -X. Refer to the Core SAP for additional details about prohibited non-study medications.

The IWRS randomization date is the reference date for "randomization". If the IWRS randomization date is missing, then the study drug start date is used.

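### The open-label compliance formula divides capsules by days, so full adherence scores 400% or 800%, and three exposure rows labelled in capsules sum milligrams

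*SAP*

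**What the plan says.** **OL compliance (SAP 6.2.6.2).** Compliance is 100 times the actual capsule count over the required capsule count. The actual count sums days times capsules taken per day. The required count is: "Required cumulative OL zavegepant capsule count is derived as {OL maxdate OL zavegepant start date + 1} where". A sub-bullet below it adds: "The required number of capsules per day is based on the DB treatment group". In the DB part of the same section, the required count is the number of days multiplied by a further term: "required number of capsules per day}, where". That term is 4 for the 100 mg and matching placebo groups and 8 for the 200 mg and matching placebo groups.

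**Where the rule is used.** SAP 9.1 makes this a relevant protocol deviation: "OL zavegepant capsule count compliance < 80% from OL zavegepant start to later of last scheduled OLE Phase visit or OL zavegepant end". SAP 6.2.4.1 puts the deviations in a frequency table, with zero counts shown, and adds: "A by-subject listing of relevant protocol deviations is provided for the full analysis set". SAP 8 says: "All TLFs described in this SAP are produced for the LSLV final CSR".

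**Exposure rows (SAP 6.2.6.1).** The DB table has this row: "Total DB study drug exposure (capsules) summed across all subjects, derived by summing cumulative DB study drug exposure across all subjects". Cumulative DB exposure is defined a few bullets above in mg, using 25 mg per capsule for zavegepant kits and 0 otherwise. The corresponding capsule rows of the OL table and the DB-or-OL table are both derived from cumulative DB exposure.

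**The concern.** The OL compliance ratio has capsules on top and days underneath, so it is too large by a factor of 4 or 8 and the 80% threshold loses its meaning. In the current SAP, the compliance categories are defined only to feed the relevant protocol deviations. The deviation table and listing are therefore the only planned outputs that report OL capsule compliance. A count near zero there would look like excellent adherence over a phase of up to 52 weeks.

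The three capsule rows have a conflict of units: the label says capsules and the quantity summed is mg. The OL row also takes its value from the wrong phase, so subjects who had placebo in the DB phase contribute nothing to their own OL total. The DB row prints zero for the placebo columns, although SAP 4.1 counts placebo as DB study drug and placebo subjects take 4 or 8 capsules a day.

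One label is also wrong. The OL overdosing category in 6.2.6.2 is headed as more than 1 capsule on a day, which describes every adherent subject. The criterion beneath it and the wording in 9.1, "More than the required number of OL zavegepant capsules taken on any 1 day", are right.

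**Working it through.** **Check against the SAP's own example.** SAP 9.4 gives a 100 mg subject with records of 3 days × 4, 4 days × 4, 3 days × 8 and 1 day × 4 capsules:

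12 + 16 + 24 + 4 = 56 capsules, which agrees with the SAP's figure. The records span 13 days.

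- DB-style formula: 100 × 56 / (13 × 4) = 107.7%
- OL formula as written: 100 × 56 / 13 = 430.8%

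**Compliance in general.** Let D be the days from OL start to OL maxdate, k the required capsules per day (4 or 8), and f the fraction of required capsules taken.

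- As written: 100 × (D × k × f) / D = 100 × k × f
- With the missing term: 100 × (D × k × f) / (D × k) = 100 × f

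| True adherence f | 100 mg (k = 4), as written | 200 mg (k = 8), as written | Corrected |
|---|---|---|---|
| 1.00 | 400% | 800% | 100% |
| 0.50 | 200% | 400% | 50% |
| 0.20 | 80% | 160% | 20% |
| 0.10 | 40% | 80% | 10% |

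The deviation fires only when k × f < 0.8, that is, below 0.8 capsules a day: f < 0.20 on 100 mg or f < 0.10 on 200 mg. These figures take OL maxdate as the last dosing date. A final visit after the last dose lowers them slightly.

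**DB capsule row.** Assumptions: planned numbers (480, 480, 240, 240), 84 days, full adherence, and the capsule label taken as right.

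| Group | Capsules | Sum as written (mg) |
|---|---|---|
| Zavegepant 100 mg | 480 × 84 × 4 = 161,280 | 161,280 × 25 = 4,032,000 |
| Zavegepant 200 mg | 480 × 84 × 8 = 322,560 | 322,560 × 25 = 8,064,000 |
| Placebo pooled | 240 × 84 × 4 + 240 × 84 × 8 = 241,920 | 0 |

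**OL capsule row, per fully adherent subject.** As written, a subject who had 84 days of DB zavegepant contributes 84 × 4 × 25 = 8,400 or 84 × 8 × 25 = 16,800. A former placebo subject contributes 0. The true OL counts are:

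- 364 days: 364 × 4 = 1,456 or 364 × 8 = 2,912, so the row is 5.8-fold too high
- 182 days: 728 or 1,456, so it is 11.5-fold too high

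**OL capsule row, total.** Assume 1,200 OLE subjects (the protocol's estimate) split 2:2:1:1, giving 400, 400, 200 and 200.

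- As written: 400 × 8,400 + 400 × 16,800 = 10,080,000
- True at 364 days: 600 × 364 × 4 + 600 × 364 × 8 = 2,620,800 (ratio 3.8)
- True at 182 days: 1,310,400 (ratio 7.7)

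**DB-or-OL capsule row, per subject on zavegepant throughout.** The true count is (84 + 364) × 4 = 1,792 or (84 + 364) × 8 = 3,584. Read literally, the row gives 8,400 or 16,800. If the text is a truncation of DB or OL exposure, it gives 1,792 × 25 = 44,800 or 3,584 × 25 = 89,600, because that cumulative variable also carries the factor 25.

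**The case against.** The strongest reply is that no one would produce 400%. The line is headed as a capsule count and ends by introducing definitions. The sub-bullet giving capsules per day has no purpose except as a multiplier, and it points to the DB section, where the multiplication is shown. The SAP's revision history for Version 7 also records that this number was specified for the OL compliance calculation. All of this is true, and it settles what was meant. It does not put the term into the formula, and if the programs already follow the intent, then the SAP and the code disagree.

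The term might also have been lost in the text copy of the SAP, which drops the minus sign between the dates. That is unlikely: the minus sign is missing from the DB formula too, yet its multiplication term survives.

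On the exposure rows, the label rather than the derivation could be at fault. The DB row would then be a correct mg total, with placebo rightly at 0. That is fair, and the 25-fold figure depends on the capsule label being right. Label and derivation conflict on either reading, though, and relabelling cannot rescue an OL row that sums DB exposure. The DB-or-OL row may well be a truncation.

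It also stands that under-dosing can still be seen in the study drug listing and in average OL mg per day, that the heading error is cosmetic because the deviation outputs follow 9.1, and that the Core SAP and mock tables, which may carry further detail, are not available here.

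**Conclusion.** The concern holds. As written, the OL compliance formula overstates adherence 4-fold on 100 mg and 8-fold on 200 mg. The below-80% deviation would miss every subject between 20% (or 10%) and 80% true adherence. All three capsule-total rows conflict with their own units, and the OL row names the wrong phase.

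The compliance factors follow directly from the text. The capsule totals are illustrations. They assume planned numbers, full adherence, 84 DB days, and 182 or 364 OLE days. The study ended early, so actual OLE durations are unknown.

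The reach is one deviation category, in its table and listing, and three descriptive rows in the final report. These errors do not enter the patient-years, cumulative mg or average mg-per-day rows. No efficacy estimate, AE or LFT frequency, or analysis set is affected. It should be corrected, but it does not threaten the trial's conclusions.

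**What to change.** - **6.2.6.2, OL required count:** (OL maxdate − OL zavegepant start date + 1) × required number of capsules per day, matching the DB formula.
- **6.2.6.1, DB capsule row:** sum over subjects the actual cumulative DB capsule count already defined in 6.2.6.2. This includes placebo capsules.
- **6.2.6.1, OL capsule row:** sum over subjects the actual cumulative OL capsule count already defined there.
- **6.2.6.1, DB-or-OL capsule row:** sum days × capsules taken per day over the zavegepant kit-type records that the table's cumulative mg row already selects.
- If a total in mg is wanted, give it a separate row labelled in mg.
- **6.2.6.2, OL overdosing heading:** replace it with the wording used in 9.1.

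The cost is four formula lines and one heading in the SAP, plus the matching programs. No new data are needed, and the DB and OL capsule counts are already derived for compliance.

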#### eDiary Usage Compliance

eDiary DBT usage compliance is derived as follows for relevant protocol deviations (see Sections 6.2.4.1 and 9.1):

• DB study drug start to later of last scheduled DBT Phase visit or DB study drug end/OL zavegepant start: 100 × (total number of efficacy data days from the DB study drug start date to DB maxdate)/(total number of days from the DB study drug start date to the DB maxdate), where DB maxdate is defined previously.

## 6.2.6.3 Nonstudy Concomitant Medications

Imputed medication start and end dates are used to assign non-study medication type (previous, current, DBT concomitant, OL zavegepant concomitant, or follow-up) to all non-study medications. Refer to the Core SAP for definitions of nonstudy medication types, non-study medication counting rules in frequency tables, non-study medication start and end date imputation, and TLF contents.

The by-subject listing of nonstudy medications is provided by therapeutic class and preferred name for the enrolled analysis set. Acute migraine and prophylactic migraine medications are identified, as well as medication type.

The following conventions apply to nonstudy medications:

- Nonstudy medications are identified from those reported on the Concomitant Medication CRF
- Prophylactic migraine medications are defined as those with an indication of "prophylactic migraine medication" on the Concomitant Medications CRF.
- Acute migraine medications are defined as non-study medications with either (1) an indication of "acute migraine medication" from the Concomitant Medications CRF, or (2) preferred name containing triptan, ergotamine, lasmiditan, ubrogepant.

## **Nonstudy DBT Concomitant Medications**

Frequency tables of the following nonstudy DBT concomitant medications are provided by treatment group, zavegepant pooled, and placebo pooled for the DBT safety analysis set: all; acute migraine; prophylactic migraine. Medications are displayed in descending order of zavegepant 200 mg frequency within therapeutic class and preferred name.

#### **Nonstudy OL Zavegepant Concomitant Medications**

A frequency table of the nonstudy OL zavegepant concomitant medications is provided by OL zavegepant dose and overall for the OL zavegepant safety analysis set. Medications are displayed in descending order of overall frequency within therapeutic class and preferred name.

## 6.3 Efficacy

Efficacy endpoints are assessed by as-randomized treatment group.

Randomization is stratified using IWRS, but the randomization strata used in analyses are based on actual data. The rationale for using the actual data in analyses is that sites may erroneously report the wrong stratum in IWRS. Hence, treatment group comparisons of continuous efficacy endpoints are *adjusted* by the randomization stratum, whereas treatment group comparisons of binary efficacy endpoints are *stratified* by the randomization stratum (except in subgroup analyses). If there are sparse data within a stratum, then results may be presented unstratified.

In treatment comparisons of binary efficacy endpoints, CIs are based on a normal approximation to the binomial distribution using asymptotic standard error (ASE). Otherwise, CIs for continuous efficacy endpoints are based on the normal distribution. All CIs are 2-sided.

See Sections 7.2 and 7.3 for the definition of efficacy analysis periods and study days.

The by-subject listing of primary and secondary efficacy endpoints is provided for the full analysis set, and includes the reason for exclusion from the migraine analysis set: randomized more than once; not treated with study drug; treated with study drug and < 14 days of eDiary efficacy data in the OP; treated with study drug and < 14 days of eDiary efficacy data in all 3 months of the DBT Phase. Results for continuous endpoints are based on observed data, whereas results for binary endpoints incorporate missing data imputation. Subjects with  $\geq$  14 days of efficacy data (not necessarily consecutive) in the month defining the endpoint are flagged for secondary endpoints based on a single month.

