5.5.1 Prophylactic Migraine Medications

Subjects may use no more than 1 of the following medications with possible migraine-prophylactic effects, regardless of indication, if not otherwise prohibited by the protocol. Doses must be stable within 3 months (12 weeks) prior to the Screening Visit and throughout the study. Use of more than 1 of the following medications is prohibited within 3 months (12 weeks) prior to the Screening Visit and throughout the study.

Prophylactic migraine medications that are permitted during the study include:

- Topiramate, gabapentin
- Beta blockers (such as: atenolol, bisoprolol, metoprolol, nadolol, nebivolol, pindolol, propranolol, timolol)
- Tricyclic antidepressants (such as: amitriptyline, nortriptyline, protriptyline)
- Venlafaxine, desvenlafaxine, duloxetine, milnacipran
- Flunarizine, lomerizine
- Lisinopril, candesartan

- Clonidine, guanfacine
- Cyprohepatdine
- Methysergide
- Pizotifen
- Feverfew, magnesium (≥ 600 mg/day), riboflavin (≥ 100 mg/day)
- Botox®

The above listed medications are the only prophylactic migraine medications allowed.

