7.2 Dose and Administration

7.2.1 Method of Assigning Subject Identification

The Investigator or designee will need to access an Interactive Web-based Response System (IWRS) in order to register each subject. Initially, after informed consent is obtained at the Screening Visit, the Investigator or designee will enter the subject into the study and obtain a subject number assignment. At the Baseline Visit and subsequent visits in the DBT and OLE

Phases, container assignments will be obtained by the Investigator (or designee) via the IWRS system. This subject number must not be reused for any other participant in the study. Subjects will maintain their subject number assigned at screening, throughout the trial.

At the Baseline Visit, eligible subjects will be randomized to a treatment group (see Section 1.4.1). The randomization will be stratified by stable prophylactic migraine medication use through randomization (yes or no), as determined by site review of subjects' concomitant medication paper diary. Subjects should be categorized as "yes" if they took a specified prophylactic migraine medication > 3 months (12 weeks) before the Screening Visit and through randomization, i.e., (1) the medication start date is > 12 weeks before the Screening Visit date, **and** (2) either the medication stop date is on or after the randomization date or the medication is ongoing. Otherwise, subjects should be categorized as "no".

Subjects may not be rescreened for this study.

Study drug will be assigned via IWRS; the system will assign specific container numbers for all study drug to be dispensed to the subject. Sites will be responsible for recording the container numbers dispensed to the subject on the Drug Accountability Form provided in the Study Binder, as well as ensure appropriate documentation of dispensation in the subject's medical record.

Once a subject completes the study, or if a subject is discontinued early from the study, the Investigator or designee must access the IWRS to document discontinuation of the subject from participation in the study.

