  - ≤ 5 migraine days, if originally consented to Protocol Version 3 or lower
  - $0 \le 7$  migraine days, if originally consented to Protocol Version 4 or higher
  - $0 \ge 19$  headache days, if originally consented to Protocol Version 3 or lower
  - $\circ$   $\leq$  14 headache days, if originally consented to Protocol Version 4 or higher
  - No headache-free days, if originally consented to Protocol Version 4 or higher. A
    headache-free day is defined as a day of eDiary efficacy data that is not a headache day
    of total pain intensity (see Section 9.2.6).
  - $\circ$  ≤ 23 days of eDiary efficacy data (see Section 9.2.2).

These are assessed during the 28-day OP analysis period (see Section 7.2). Migraine days and headache days are absolute, not prorated to 28 days per month (see Sections 9.2.5 and 9.2.6), and of total pain intensity.

Protocol version for original consent is from the Inclusion/Exclusion CRF.

Relevant subject management protocol deviations include the following categories:

- Randomization stratum discrepancies between IWRS and actual data, defined as any of the following subcategories:
  - o IWRS randomization stratum of yes, but no stable prophylactic migraine medication taken through randomization
  - IWRS randomization stratum of no, but stable prophylactic migraine medication taken through randomization.

See Section 6.2.5.4 for the definition of non-study stable medication through randomization.

- Prophylactic migraine medication usage issue, defined as any of the following subcategories:
  - Prophylactic migraine medication started or stopped from 12 weeks before informed consent to randomization. Defined as informed consent date − 84 days ≤ imputed nonstudy medication start or end date ≤ IWRS randomization date.
  - > 1 prophylactic migraine medication taken on or after informed consent. "> 1" is defined as > 1 unique preferred name.
- DB study drug dosing issue, defined as any of the following subcategories (see Section 6.2.6.2):
  - DB study drug taken but not randomized
  - o More than the required number of DB capsules taken on any 1 day
  - DB capsule count compliance < 80% from DB study drug start to later of last scheduled DBT Phase visit or DB study drug end/OL zavegepant start
  - Incorrect DB study drug taken

- OL zavegepant dosing issue, defined as any of the following subcategories (see Section 6.2.6.2):

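### The SAP's 'actual' randomization stratum counts drugs by CRF indication, while the protocol most naturally stratifies on a drug list that applies regardless of indication, so some subjects can be analysed in a different stratum from the one they were correctly randomized in.

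*SAP*

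**What the plan says.** **At randomization.** Protocol 7.2.1 has sites enter 'yes' for subjects "if they took a specified prophylactic migraine medication > 3 months (12 weeks) before the Screening Visit and through randomization". It then spells this out in two date conditions: "the medication start date is > 12 weeks before the Screening Visit date", and "either the medication stop date is on or after the randomization date or the medication is ongoing". Neither condition mentions indication. The protocol's list of permitted prophylactics is in 5.5.1. It names individual drugs and classes, limits subjects to one of them "regardless of indication, if not otherwise prohibited by the protocol", and closes by saying that no others are allowed.

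**At analysis.** SAP 6.3 says that "the randomization strata used in analyses are based on actual data", because "sites may erroneously report the wrong stratum in IWRS". SAP 4.3 and 6.5 repeat the choice. SAP 6.2.5.4 sets the dates: start more than 84 days before informed consent, end on or after IWRS randomization, using imputed dates. It points to 6.2.6.3 for the drugs: "Prophylactic migraine medications are defined as those with an indication of" prophylactic migraine medication on the Concomitant Medications CRF.

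**Where the result is used.** The stratum enters the primary model, the Mantel-Haenszel responder analysis, the acute-medication model and the MSQ and MIDAS regressions. Each of these is also reported within stratum. SAP 6.2.5 cross-tabulates IWRS against actual stratum. SAP 9.1 lists disagreement in either direction as a relevant deviation, for example "IWRS randomization stratum of yes, but no stable prophylactic migraine medication taken through randomization".

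**The concern.** The SAP's reason for dropping the IWRS value is site error. That reason holds only if the replacement measures the same thing. Here the two rules can classify the same subject differently when nobody has made a mistake.

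The protocol makes such subjects likely. Exclusion criteria 2c and 2d admit stable hypertension, and depression or anxiety treated with one daily drug per disorder. The 5.5.1 list includes beta blockers, lisinopril, candesartan, tricyclics, venlafaxine and duloxetine. Someone taking long-term lisinopril recorded for hypertension takes a listed drug but has no record with the migraine-prophylaxis indication.

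Three outputs are exposed:

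- The by-stratum estimates would describe groups that do not match their labels.
- The cross table and the discrepancy deviation would mix site errors with differences of definition, and could not tell them apart.
- The deviation for taking more than one prophylactic uses the same indication-based definition. A subject on topiramate for migraine and lisinopril for hypertension breaches 5.5.1 but would not be counted.

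**Working it through.** **1. The two rules compared**

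| Element | Protocol 7.2.1 with 5.5.1 | SAP 6.2.5.4 with 6.2.6.3 |
|---|---|---|
| Drugs that count | Specified prophylactic; list applies whatever the indication | CRF indication only |
| Start | More than 12 weeks before Screening Visit | More than 84 days before informed consent |
| End | On or after randomization, or ongoing | Imputed end on or after IWRS randomization |
| Source | Site review of paper diary | Concomitant Medications CRF, imputed dates |

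**2. The date anchor.** If consent falls g days before Screening, the rules disagree only for drugs started 85 to 84 + g days before Screening, always from 'yes' to 'no'. With g = 0 nobody moves; with g = 7 the range is 85 to 91 days. Protocol 7.2.1 places consent at the Screening Visit, so this normally has no effect. The drug definition is the difference that matters.

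**3. The plan's power figure.** Inputs from SAP 5: 440 per zavegepant group, 2 × 220 = 440 pooled placebo, difference 1 day, SD 4.2, two-sided alpha 0.025. SE = 4.2 × √(2/440) = 0.283. Power = Φ(1/0.283 − 2.241) = 90.15%, which reproduces the stated 90% or more. The formula has no stratum term, so the choice of stratum does not alter it.

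**4. How many could move.** The documents give no figures, so these are assumptions: p = 30–40% truly 'yes', and f = 20–40% of those on a listed drug for another indication only. The moved share is p × f, from 0.30 × 0.20 = 6% to 0.40 × 0.40 = 16%, or about 26 to 70 per 440.

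**5. Effect on the overall comparison.** Let N = 1 − p(1 − f) be the share analysed as 'no', r = pf/N the share of those who are truly 'yes', and b the difference in mean outcome between strata (assumed 0.5 to 2 days). Taking 4.2 as the within-stratum SD, the SE ratio is √(1 + b²·N·r(1 − r)/4.2²).

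| p | f | N | r | SE ratio, b = 0.5 | b = 1 | b = 2 |
|---|---|---|---|---|---|---|
| 0.30 | 0.20 | 0.76 | 0.079 | 1.0004 | 1.0016 | 1.006 |
| 0.30 | 0.40 | 0.82 | 0.146 | 1.0007 | 1.0029 | 1.012 |
| 0.40 | 0.20 | 0.68 | 0.118 | 1.0005 | 1.0020 | 1.008 |
| 0.40 | 0.40 | 0.76 | 0.211 | 1.0009 | 1.0036 | 1.014 |

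A simulation (3,000 runs, 440 versus 440, 30% 'yes', stratum effect 1 day, true difference −1) moved 0, 5, 10 and 20% of the 'yes' stratum to 'no'. The mean estimate stayed between −1.007 and −1.000, the mean SE between 0.2831 and 0.2838, and power between 0.897 and 0.902. Even if the analysis stratum carried no information at all (20–50% 'yes', b up to 2 days), power would be 88.4% to 90.1%.

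**6. Effect on the by-stratum estimates.** Assume true benefits of 1.3 days in 'no' and 0.5 days in 'yes'. The estimate labelled 'no' then targets 1.3 − 0.8r: 1.24 days at r = 0.079 and 1.13 days at r = 0.211, a shift of 0.06 to 0.17 days. With N = 0.76, about 334 per arm are analysed as 'no', and the SE is 4.2 × √(2/334) = 0.325. The shift is therefore about 0.2 to 0.5 of a standard error. If the true effect is the same in both strata, there is no shift.

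**The case against.** Four points can fairly be made for the plan.

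- **The link to 5.5.1 is inferred.** Protocol 7.2.1 says 'specified' without a cross-reference, and the phrase about indication in 5.5.1 belongs to a limit on concurrent use. This stands as a caution. But 5.5.1 is the natural referent: it is the protocol's list of permitted prophylactics. The other drug list, Appendix 4, serves to define prior non-response.
- **Sites may have used the CRF indication for any listed drug.** Then no one would be reclassified. Neither the CRF instructions nor the Core SAP, which holds the date-imputation rules, is available. This stands, and it is why the size is unknown.
- **Using the actual stratum is legitimate and disclosed.** SAP 4.3 and 6.3 say so and 6.3 gives the reason. Protocol 9.3.1.1 names the randomization stratum without saying whether it is the IWRS or the actual value. A reader might infer that the SAP contradicts the protocol model, or that IWRS must be the main stratum. The documents support neither; the second is a debatable preference that would leave genuine entry errors in the main model.
- **Discordance is already shown.** The cross table and deviation listing would reveal how many subjects differ. They would not reveal why, and that is the gap.

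**Conclusion.** The mismatch in definitions is real, and its consequences are limited. On the natural reading of 'specified', a subject on a stable listed drug for another indication can be correctly 'yes' in IWRS, 'no' in every efficacy and outcomes model, and a reported discrepancy.

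A reader might go further and infer that correctly stratified subjects have in fact been moved, or that the primary result is compromised. The documents show only that reclassification can happen. Nor is the overall comparison biased: the derived stratum is defined by medication use up to randomization, and the loss is a standard-error increase of about 1.4% at most under the assumptions above. SAP 5 evaluates no significance, so no testing decision turns on it.

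What remains is the labelling of the by-stratum estimates, the meaning of the cross table, and the accuracy of the deviation counts, which could err in both directions. The estimates of 6–16% reclassified and a 0.06–0.17 day shift rest entirely on assumed inputs. The point is worth correcting because estimates and intervals, including those by stratum, are now what the report delivers.

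**What to change.** - **Drug definition.** In SAP 6.2.5.4 and 6.2.6.3, derive the actual stratum from the Protocol 5.5.1 drugs by preferred name, regardless of indication. SAP 6.2.6.3 already uses preferred names alongside indication for acute drugs. Fix the list of names before the LSLV database lock, because 5.5.1 gives several classes by example. Magnesium and riboflavin carry dose thresholds there, so they also need the recorded dose.
- **Date anchor.** Use the Screening Visit date, as in Protocol 7.2.1.
- **Deviations.** Apply the same definition in SAP 9.1 to the stratum discrepancies and the prophylactic-medication usage items.
- **Sensitivity run.** Repeat the primary and secondary models, including the responder, MSQ and MIDAS analyses, with the IWRS stratum.
- **If the indication rule is intended,** say so in the SAP and state that the cross table and discrepancy counts include differences of definition as well as site errors.

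The cost is SAP wording, some programming for the name list, and one extra set of model output. The IWRS stratum is already needed for the cross table, so no new data are required.
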